2.2.2 Inclusion Criteria

Patients are eligible to be included in the study only if all of the following criteria apply:

1. Male or female patients 18 to 75 years of age inclusive, at the time of signing the informed consent
2. Patients with physician's confirmed diagnosis of severe asthma with an eosinophilic phenotype, ie, diagnosis of severe asthma in preceding at least 12 months, with an eosinophil count of ≥ 300 cells/ μ L at screening, requiring treatment with high-dose ICS (>500 μ g fluticasone propionate dry powder formulation, or >800 μ g budesonide dry powder formulation, or equivalent total daily dose) and a LABA as maintenance treatment for at least 3 months prior to enrolment
3. A decreased lung function with prebronchodilator (Pre-BD) forced expiratory volume in 1 second (FEV1) of $<80\%$ predicted, demonstrated by spirometry at screening
4. At least 2 documented asthma exacerbations in the preceding 12 months, except in 30 days before the date of informed consent, that required the use of a systemic corticosteroid or temporary increase from the patient's usual maintenance dose of OCS

Document Title:	Document ID:	BP04-01
Statistical Analysis Plan	Version Number:	3.1
	Effective Date:	25-Nov-2021

5. Documented postbronchodilator (post-BD) reversibility in FEV1 of $\geq 12\%$ and ≥ 200 mL in FEV1 within 12 months before first dose. If historical documentation is not available, reversibility must be demonstrated and documented at screening or Day 1 before first dose
6. Benralizumab naive patients who have not previously received benralizumab prior to the start of this study
7. Patients who are willing and capable of giving signed informed consent as described in Appendix A, which includes compliance with the requirements and restrictions listed in the informed consent form (ICF) and in this protocol.

2.2.3 Exclusion Criteria

[figure not shown]
Patients will be excluded from the study if any of the following criteria apply:

1. Clinically important pulmonary disease other than asthma (eg, active lung infection, chronic obstructive pulmonary disease, bronchiectasis, pulmonary fibrosis, cystic fibrosis etc.) or ever been diagnosed with pulmonary or systemic disease, other than asthma, that are associated with elevated peripheral eosinophil counts (eg, allergic bronchopulmonary aspergillosis/mycosis, Churg-Strauss syndrome, hypereosinophilic syndrome), which can confound the outcome assessment
2. Patients currently enrolled in an interventional clinical study in parallel including those with any biologic treatment
3. Patients who have received any biologic within 30 days prior to the date of informed consent.
4. Known history of allergy or reaction to the benralizumab formulation or excipients (L-histidine, L-histidine hydrochloride monohydrate, α -trehalose dihydrate, polysorbate 20, water for injection)
5. History of anaphylaxis to any biologic therapy
6. A helminthic parasitic infection diagnosed within 24 weeks before the date informed consent is obtained that has not been treated with, or has failed to respond to, standard of care therapy
7. Acute asthma exacerbation 30 days before the date informed consent
8. Acute asthma exacerbation between screening and first dose of study dose administration.
9. Acute upper or lower respiratory infections requiring antibiotics or antiviral medication within 30 days before the date informed consent
10. Patients with malignancy within 5 years prior to enrolment, with the exception of adequately treated in-situ carcinoma of the cervix, uteri, basal, or squamous cell carcinoma or non-melanomatous skin cancer with active or recent malignancy

Document Title:	Document ID:	BP04-01
Statistical Analysis Plan	Version Number:	3.1
	Effective Date:	25-Nov-2021

11. Any clinically significant abnormal findings in physical examination, vital signs, haematology, clinical chemistry, or urinalysis, which, in the opinion of the investigator, may put the participant at risk because of his/her participation in the study
12. History of current alcohol, drug, or chemical abuse or past abuse that would impair or risk the participant's full participation in the study, in the opinion of the investigator
13. Female patients who are pregnant or lactating or planning a family during the study period.

2.2.4 Study Flow chart

EOS = end of study

Document Title:	Document ID:	BP04-01
Statistical Analysis Plan	Version Number:	3.1
	Effective Date:	25-Nov-2021

not logically possible, sufficient time as per clinician discretion should be allotted between phlebotomy and vital signs assessment. For details, please refer to Section 8.1.3.

- e. When historical proof of postbronchodilator reversibility in FEV1 is not documented within 12 months before Visit 1, the reversibility test by spirometry will need to be performed either during screening or on Day 1 before first dose.
- f. While on study drug treatment and within 2 months after the end of study treatment/discontinuation of the study drug.
- g. Participants will be provided a patient diary to record any undesirable health-related experience or adverse events occurring during the study. Adverse events and serious adverse events mentioned both in the patient diary and verbally communicated by the participant will be recorded.

2.3 Randomization

Not Applicable

2.4 Blinding and Un-Blinding

Not Applicable

2.5 Interim Analysis

No interim analyses is planned for this study.

3. Population Analysis Set

3.1 Enrolled Analysis Set

"Enrolled" means a participant's, or their legally authorised representative's, agreement by signing the ICF to participate in a clinical study following completion of the informed consent process.

3.2 Assigned to Study intervention Analysis Set

Potential participants who fulfil the eligibility criteria and are assigned with the study identification number.

3.3 Evaluable Analysis Set

All participants assigned to study intervention and receiving at least 1 dose of study intervention and provide at least one post baseline assessment.

3.4 Safety Analysis Set

All participants assigned to study intervention and who take at least 1 dose of study intervention.

4. Sample Size and Power Calculations

The primary objective of this study is to assess safety and tolerability of benralizumab in adult (18 to 75 years of age) male or female patients who have severe asthma with eosinophilic phenotype requiring high dose of ICS and LABA.

Document Title:	Document ID:	BP04-01
Statistical Analysis Plan	Version Number:	3.1
	Effective Date:	25-Nov-2021

Based on the literature review, the below table is created for listing the key AEs (headache, pyrexia, pharyngitis and injection site reactions) and hypersensitivity reactions (e.g. anaphylaxis, angioedema, urticaria, urticaria papular, rash) which were included in the USPI, SmPC and the India PI, all in the range of 1% to 10%.

Key AE Terms	Incidence Rate (%)		
	SmPC/ India label	USPI	SIROCCO
Headache	Common (1%-10%)	8%	7%-9%
Pharyngitis		5%	4%-6%
Pyrexia		3%	3%-4%
Injection site reactions		2.2%	2%-4%
Hypersensitivity		3%	3%

$$\text{Effectiveness } n = \frac{z^2 p (1-p)}{d^2}$$

where n = calculated sample size, Z = tabulated Z statistic value for α level of confidence, P = expected proportion of AEs and d = absolute precision level (half-width of the confidence interval [CI]).

Considering the maximum limit of the incidence rate of AEs to be 10%, approximately 139 evaluable participants will be required to present 95% CI around the estimated AE incidence rate with absolute precision level of 0.05. Considering dropout rate of 5%, a total of 147 participants will be required to be enrolled into the study.

5. Patient Characteristics and Study Conduct Summaries

5.1 General Considerations

Statistical Analysis will be performed using SAS (version 9.4 or higher) software (SAS Institute Inc USA). Categorical variables will be summarized with the frequency, percentage of Patients in each category and corresponding 95% CI (using Clopper-Pearson exact Method, where appropriate). Continuous variables will be summarized descriptively with the number of Patients, mean, standard deviation, median, 25th and 75th percentiles and minimum and maximum values.

5.2 Decimal Point

Unless otherwise noted, means, median, will be presented to one decimal place more than the measured value, the same decimal as the measured value, percentages, 25th and 75th percentiles and 95% confidence intervals will be presented to two decimal places and p-value will be presented to three decimal place. Percentages after zero counts will not be displayed and percentages equating to 100% will be presented as 100%, without any decimal places.

5.3 Disposition of Patients

Patient disposition table will be based on all Evaluable Analysis Set who consented to participate in the study. The following summaries will be included in the disposition table: total number of Patient Enrolled in the study, total

Document Title:	Document ID:	BP04-01
Statistical Analysis Plan	Version Number:	3.1
	Effective Date:	25-Nov-2021

number of Patients screened in the study, number of Patients who failed screening, number and percentage of Patients who completed the study and number and percentage of Patients who discontinued from the study with reason for discontinuation.

5.4 Demographic and Baseline Characteristics

Demographic and baseline characteristics will be summarized based on the Evaluable Analysis Set.

Descriptive summaries will be provided for the demographic and baseline characteristics. Demographic characteristics and baseline characteristics such as age, Gender and Race, etc. will be summarized and tabulated for Evaluable Analysis Set.

All the continuous variables will be summarized by n, mean, standard deviation, median, 25th and 75th percentiles and minimum and maximum values. All the categorical variables will be summarized as frequency, percentage of Patients in each category and corresponding 95% CI (using Clopper-Pearson exact Method, where appropriate).

5.5 Covid-19 Vaccination

Covid-19 Vaccination will be summarized based on the Evaluable Population.

Descriptive summaries will be provided for the Covid-19 Vaccination.

All the continuous variables will be summarized by n, mean, standard deviation, median, 25th and 75th percentiles and minimum and maximum values. All the categorical variables will be summarized as frequency, percentage of Patients in each category and corresponding 95% CI (using Clopper-Pearson exact Method, where appropriate).

5.6 Medical History

Medical History will be summarized based on the Evaluable Population.

Descriptive summaries will be provided for the Medical History.

All the continuous variables will be summarized by n, mean, standard deviation, minimum, median and maximum values. All the categorical variables will be summarized as frequency, percentage of Patients in each category and corresponding 95% CI (using Clopper-Pearson exact Method, where appropriate).

5.7 Electrocardiogram (ECG)

Electrocardiogram will include Heart rate, QRS, PR, RR, QT, QTcB. Electrocardiogram will be summarized based on the Safety Analysis Set.

Descriptive summaries will be provided for the Electrocardiogram.

All the continuous variables will be summarized by n, mean, standard deviation, median, 25th and 75th percentiles and minimum and maximum values. All the categorical variables will be summarized as frequency, percentage of Patients in each category and corresponding 95% CI (using Clopper-Pearson exact Method, where appropriate).

Document Title:	Document ID:	BP04-01
Statistical Analysis Plan	Version Number:	3.1
	Effective Date:	25-Nov-2021

6. Endpoints Analysis Strategy

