### **6.4 Limitations of the Study**

This study has no control group and will follow about 147 patients during the period of 24 weeks. Given these conditions, the safety and effectiveness data available for collection may be limited compared with randomised clinical trials. The data generated by the study will be used to meet the post-approval commitment and presented in descriptive way. The descriptive data will be published only locally. This study will generate results from a wider range of data than those previously derived from the more limited clinical trial setting. This study will provide information on the Indian patient population that is treated with Fasenra.

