- The small "n" in summary statistics represents the total number of patients.
- Percentages are based on number of Safety Analysis Set.
- SD = Standard Deviation, min=minimum, max=maximum
- Programmer Note: Visit x: Screening Visit, Visit 2 and Visit 5
- Source: Listing 16.3.5

Document Title:	Document ID:	BP04-01
Statistical Analysis Plan	Version Number:	3.1
	Effective Date:	25-Nov-2021

Table 14.3.5. Summary of Targeted Physical Examination (Safety Analysis Set)

	N = xx
	n (%)
Visit x	
Physical Examination Performed	
Yes	xx (xx.xx)
No	xx (xx.xx)
General Appearance	
Normal	xx (xx.xx)
Abnormal	xx (xx.xx)
If Abnormal	
Abnormal CS	xx (xx.xx)
Abnormal NCS	xx (xx.xx)
Respiratory System	
Normal	xx (xx.xx)
Abnormal	xx (xx.xx)
If Abnormal	
Abnormal CS	xx (xx.xx)
Abnormal NCS	xx (xx.xx)
Cardiovascular System	
Normal	xx (xx.xx)
Abnormal	xx (xx.xx)
If Abnormal	
Abnormal CS	xx (xx.xx)
Abnormal NCS	xx (xx.xx)
Abdomen	
Normal	xx (xx.xx)
Abnormal	xx (xx.xx)
If Abnormal	
Abnormal CS	xx (xx.xx)
Abnormal NCS	xx (xx.xx)
Skin	
Normal	xx (xx.xx)
Abnormal	xx (xx.xx)
If Abnormal	
Abnormal CS	xx (xx.xx)
Abnormal NCS	xx (xx.xx)
Head, Eye, Ear, Nose, Throat	
Normal	xx (xx.xx)
Abnormal	xx (xx.xx)
If Abnormal	
Abnormal CS	xx (xx.xx)
Abnormal NCS	xx (xx.xx)
Lymph Node	
Normal	xx (xx.xx)
Abnormal	xx (xx.xx)
If Abnormal	
Abnormal CS	xx (xx.xx)
Abnormal NCS	xx (xx.xx)
Thyroid	
Normal	xx (xx.xx)

Document Title:	Document ID:	BP04-01
Statistical Analysis Plan	Version Number:	3.1
	Effective Date:	25-Nov-2021

Abnormal	xx (xx.xx)
If Abnormal	
Abnormal CS	xx (xx.xx)
Abnormal NCS	xx (xx.xx)
Musculoskeletal System	
Normal	xx (xx.xx)
Abnormal	xx (xx.xx)
If Abnormal	
Abnormal CS	xx (xx.xx)
Abnormal NCS	xx (xx.xx)
Neurological System	
Normal	xx (xx.xx)
Abnormal	xx (xx.xx)
If Abnormal	
Abnormal CS	xx (xx.xx)
Abnormal NCS	xx (xx.xx)
Other	
Normal	xx (xx.xx)
Abnormal	xx (xx.xx)
If Abnormal	
Abnormal CS	xx (xx.xx)
Abnormal NCS	xx (xx.xx)

- The Capital "N" in the column header represents the total number of patients in Safety Analysis Set.
- The small "n" in summary statistics represents the total number of patients.
- All Percentages rows are based on the total number of Safety Analysis Set.
- Programmer note: Visit x: Screening Visit, Visit 1, Visit 2, Visit 3, Visit 4 and Visit 5.
- Source: Listing 16.3.6

Document Title:	Document ID:	BP04-01
Statistical Analysis Plan	Version Number:	3.1
	Effective Date:	25-Nov-2021

Table 14.3.6.1. Summary of Serum Pregnancy Test (Safety Analysis Set)

	N = xx

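### The only rate-corrected QT in the SAP's ECG summary is QTcB, so a heart-rate shift between visits can move it without any change in repolarisation; QTcF can be derived from the listed QT and RR and shown beside it

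*SAP*

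**What the plan says.** SAP section 5.7 lists the ECG variables: "Electrocardiogram will include Heart rate, QRS, PR, RR, QT, QTcB". It names the analysis set, "Electrocardiogram will be summarized based on the Safety Analysis Set", and the type of analysis, "Descriptive summaries will be provided for the Electrocardiogram". It states no test, no QTc threshold and no change from baseline.

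The note closing the ECG mock table (Table 14.3.4) fixes the time points: "Programmer Note: Visit x: Screening Visit, Visit 2 and Visit 5". These match the protocol's Schedule of Activities, which places the ECG at screening, Week 4 and Week 24. The protocol names no correction formula, so the choice of QTcB is made in the SAP, without a stated reason. No other QT correction appears in either document.

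Protocol section 6.4 describes the setting: "This study has no control group and will follow about 147 patients during the period of 24 weeks".

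**The concern.** QT shortens as heart rate rises, so a corrected QT is useful only if the correction removes that dependence. Bazett's formula divides QT by the square root of RR. If the true relation is flatter than a square root, QTcB over-corrects at higher rates and under-corrects at lower ones. It then falls when heart rate falls and rises when heart rate rises, with repolarisation unchanged.

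Heart rate could move between visits here. Participants have severe asthma, use a LABA, and may improve on treatment; protocol section 6.6.1 also lets the investigator change the ICS-LABA dose with documented justification. A falling rate could hide some QT lengthening in the QTcB summary, and a rising rate could imitate it. With one arm, no comparator carries the same rate shift. Safety is the primary objective, so the ECG summary should be readable on its own terms, and a second correction needs nothing beyond the QT and RR already listed.

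**Working it through.** The documents give no QTc figure, so there is nothing of the plan's own to reproduce. The sample-size figures (139 evaluable, 147 enrolled) concern adverse-event incidence and play no part in this point.

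**Inputs from the documents.** QT, RR, heart rate and QTcB are listed in SAP section 5.7. The ECG visits are Screening, Week 4 (Visit 2) and Week 24 (Visit 5). There is no control arm.

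**Assumptions, not in the documents.** A corrected QT of 410 ms at 60 beats/min; a fall in heart rate from 90 to 78 beats/min; a QT-RR exponent b, varied over 0.25, 1/3, 0.40 and 0.50. QTcB is read as Bazett.

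**Formulas.** RR = 60/HR in seconds. Holding repolarisation constant means QT = 410 × RR^b. Then:

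- QTcB = QT/RR^(1/2) = 410 × RR^(b − 1/2)
- QTcF = QT/RR^(1/3) = 410 × RR^(b − 1/3)

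**Numbers.** RR is 60/90 = 0.667 s before and 60/78 = 0.769 s after. At b = 1/3, QT is 358.2 ms and then 375.7 ms. QTcB goes from 358.2/√0.667 = 438.7 ms to 375.7/√0.769 = 428.3 ms, a shift of about −10 ms, while QTcF stays at 410.0 ms. Across the exponents:

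| b | QTcB at 90 (ms) | QTcB at 78 (ms) | QTcB shift (ms) | QTcF at 90 (ms) | QTcF at 78 (ms) | QTcF shift (ms) |
|---|---|---|---|---|---|---|
| 0.25 | 453.7 | 437.8 | about −16 | 424.1 | 419.1 | about −5 |
| 1/3 | 438.7 | 428.3 | about −10 | 410.0 | 410.0 | 0 |
| 0.40 | 427.0 | 420.9 | about −6 | 399.1 | 402.9 | about +4 |
| 0.50 | 410.0 | 410.0 | 0 | 383.2 | 392.5 | about +9 |

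A rise from 78 to 90 gives the same shifts with the sign reversed.

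**Reading the table.** Every shift is an artefact, because repolarisation was held fixed. QTcB is free of it only at b = 0.50, and QTcF only at b = 1/3. The residual exponents are b − 1/2 and b − 1/3, equal in size at b = (1/2 + 1/3)/2 ≈ 0.42. Below that value QTcF depends less on rate; above it QTcB does. For b strictly between 1/3 and 1/2 the two artefacts have opposite signs, so disagreement between the two summaries is itself a sign that heart rate has moved.

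**The case against.** The strongest case against runs as follows.

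- **The size is assumed.** Holding QTcF constant and showing that QTcB moves presupposes that Fridericia is right. This stands, which is why the result is given across exponents; at b = 0.50 QTcF is the one in error. The heart-rate change is also assumed, and to move a mean it would have to be a shift across the cohort. Section 6.6.1 asks for stable controller doses, and exclusions 7 and 8 remove patients with an exacerbation in the 30 days before consent or between screening and first dose. Both make a large mean shift less likely.
- **Rate information is already there.** Heart rate, RR and uncorrected QT are summarised with QTcB, so a reader can see that the rate moved. This stands. However, separate means do not give a second QTc: QTcF has to be computed per participant and cannot be recovered exactly from summary means and SDs.
- **No conclusion depends on it.** ECG is not a named endpoint in SAP section 6.1. The paired tests in section 6.3.1 cover vital signs and laboratory values, not ECG. Listing 16.3.5 flags each patient's ECG results for abnormality and clinical significance, and protocol section 8.1.2 sends clinically significant new findings to AE reporting. This stands and keeps the point minor.
- **No QT concern is identified.** The potential risks in protocol section 2.3.1 include none of cardiac repolarisation. This also stands.

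A reader might infer that a rate-driven QTcB shift cannot be told apart from a drug effect. The documents do not support that, because the rate variables are reported alongside. Nor would QTcF settle attribution: with no control arm, a change in QTcF could not be assigned to the drug either.

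**Conclusion.** The point holds as a minor gap in a descriptive safety summary. Relying on QTcB alone is safe from rate artefact only if QT varies with the square root of RR in this population, and neither document argues that it does. For an assumed 12 beats/min fall the artefact ranges from about −16 ms to none, depending on an exponent the documents do not give.

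Two stronger readings should be resisted. One is that a heart-rate change necessarily produces a spurious shift of a known size; at an exponent of 0.50 there is none. The other is that QTcF should displace QTcB as the main summary; nothing in the documents shows that it fits these patients better, and above about 0.42 it is the more rate-dependent of the two. What is supported is reporting both.

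Most of mock Table 14.3.4 is missing from the text available, so its rows could not be checked. The finding rests on section 5.7. Sample size and data collection are unaffected.

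**What to change.** In SAP section 5.7 and Table 14.3.4:

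- derive QTcF = QT/RR^(1/3), with RR in seconds, for each participant at Screening, Visit 2 and Visit 5;
- summarise it next to QTcB and heart rate on the Safety Analysis Set;
- add QTcB and QTcF, with their formulas, to the abbreviation list.

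The cost is one derived variable and one additional table row, with no new measurement.

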6.1 Endpoints Analysis

6.1.1 Primary Endpoint

- Percentage of AEs, SAEs and TEAEs
- Nature, Incidence and Severity of AES, Including unexpected adverse drug reactions
- Percentage of patients with AEs that lead to Study treatment discontinuations or modifications

6.1.2 Secondary Endpoint

- Time to first asthma exacerbation
- Annualised exacerbation rate
- Overall investigators assessment on the outcome of the treatment: "well controlled", "Partly Controlled" and "Uncontrolled"
- Change in blood eosinophil levels from baseline at week 4, 16 and 24.

6.2 Efficacy Hypothesis

There is no statistical hypothesis to be tested in this study.

6.3 Statistical Methods for Efficacy Analysis

Statistical Analysis will be performed using SAS (version 9.4 or higher) software (SAS Institute Inc USA). Categorical variables will be summarized with the frequency and percentage of Patients in each category. Continuous variables will be summarized descriptively with the number of Patients, mean, standard deviation, 25th and 75th percentiles, minimum, median and maximum values.

6.3.1 Primary Endpoint Analysis

The primary analysis for primary endpoint will be based on Safety Analysis Set.

Primary Endpoint evaluations will include Adverse Events (AEs), Serious Adverse Events (AEs), Treatment Emergent Adverse Event (TEAEs), Participants with unexpected Adverse Drug Reactions (ADRs) and Participants with AEs that lead to study treatment discontinuations or modifications.

Adverse Events (AEs), Serious Adverse Events (AEs), Treatment Emergent Adverse Event (TEAEs), Participants with unexpected Adverse Drug Reactions (ADRs) and Participants with AEs that lead to study treatment discontinuations or modifications will be summarized using Frequency, Percentages and 95% CIs (using Clopper-Pearson Exact method).

Document Title:	Document ID:	BP04-01
Statistical Analysis Plan	Version Number:	3.1
	Effective Date:	25-Nov-2021

The AE profiles in participants will be presented as summaries showing the number of participants (n, %) along with number of events by System Organ Class and Preferred Terms assigned to the event by Medical Dictionary for Regulatory Activities (MedDRA) for the following:

- TEAEs
- SAEs
- Related and non-related TEAEs
- Serious and non-serious TEAEs
- TEAEs based on severity (Mild, Moderate, Severe)
- Unexpected ADRs based on severity (Mild, Moderate, Severe)

Physical Examination will include General Appearance, Respiratory system, Cardiovascular system, Abdomen, Skin, Head, Eye, Ear, Nose, Throat, Lymph node, Thyroid, Musculoskeletal system and Neurological System. Physical Examination will be summarized based on the Safety Analysis Set.

Descriptive summaries will be provided for the Physical Examination.

All the continuous variables will be summarized by n, mean, standard deviation, minimum, median and maximum values. All the categorical variables will be summarized as frequency, percentage of Patients in each category and corresponding 95% CI (using Clopper-Pearson exact Method, where appropriate).

Vital Signs will include Pulse rate, Respiratory rate, Systolic Blood Pressure, Diastolic Blood Pressure and Temperature.

Vital Signs will be summarized based on the Safety Analysis Set.

Vital Signs will be summarised descriptively for actual values and change from baseline values for each visit using the number of observations, arithmetic mean, SD, median, 25th and 75th percentiles, and minimum and maximum values.

The Vital signs (Pulse rate, Respiratory rate, Systolic Blood Pressure, Diastolic Blood Pressure and Temperature) in this study is to evaluate the change from baseline to Post-baseline will be analysed using Paired t – test / Wilcoxon signed-rank test at 5% level of significance.

Change from baseline will be determined as:

Change from Baseline = (Post-baseline – Baseline)

Percent Change Change from Baseline = ([Post-baseline – Baseline] / Baseline) X 100

Clinical Safety laboratory Assessment will include clinical chemistry, haematology and urinalysis. Clinical Safety laboratory assessment will be summarized based on the Safety Analysis Set.

Document Title:	Document ID:	BP04-01
Statistical Analysis Plan	Version Number:	3.1
	Effective Date:	25-Nov-2021

Clinical Safety laboratory Assessment will be summarised descriptively for actual values and change from baseline values for each visit using the number of observations, arithmetic mean, SD, median, 25th and 75th percentiles, and minimum and maximum values.

The Clinical Safety Laboratory (If available) in this study is to evaluate the change from baseline to Post-baseline will be analysed using Paired t – test / Wilcoxon signed-rank test at 5% level of significance.

Change from baseline will be determined as:

Change from Baseline = (Post-baseline – Baseline)

Percent Change Change from Baseline = ([Post-baseline – Baseline] / Baseline) X 100

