## 9.4.2 Safety

### 9.4.2.1 Primary Endpoints

In order to assess safety and tolerability of benralizumab in participants with severe eosinophilic asthma, following results will be presented:

Frequency, percentage, and 95% CIs (using Clopper-Pearson exact method) will be reported for the following:

- AEs
- SAEs
- TEAEs
- Participants with unexpected Adverse Drug Reactions (ADRs)
- Participants with AEs that lead to study treatment discontinuations or modifications.

The AE profiles in participants will be presented as summaries showing the number of participants (n, %) along with number of events by System Organ Class and Preferred Terms assigned to the event by Medical Dictionary for Regulatory Activities (MedDRA) for the following:

- TEAEs
- SAEs
- Related and non-related TEAEs
- Serious and non-serious TEAEs
- TEAEs based on severity (Mild, Moderate, Severe)
- Unexpected ADRs based on severity (Mild, Moderate, Severe)

The physical examination, vital signs, and laboratory parameters (if available) will be summarised descriptively for actual values and change from baseline values for each visit using the number of observations, arithmetic mean, SD, median, 25th and 75th percentiles, and minimum and maximum values.

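### The SAP drops, without declaring it, the protocol's change-from-baseline summary for physical examination, and Table 14.3.5 divides every visit's counts by the whole Safety set

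*SAP*

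**What the plan says.** **Protocol.** Section 9.4.2.1 puts three kinds of data under one rule: "The physical examination, vital signs, and laboratory parameters (if available) will be summarised descriptively for actual values and change from baseline values for each visit". Section 9.4.1 defines baseline as the last measurement before the first dose. Sections 8.1.1 and 8.1.2 send new or aggravated examination and ECG findings to adverse event reporting when the investigator judges them clinically significant.

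**SAP text.** Section 6.3.1 carries the rule over for vital signs ("Vital Signs will be summarised descriptively for actual values and change from baseline values for each visit") and, in matching terms, for laboratory data. For physical examination it says only "Descriptive summaries will be provided for the Physical Examination". Section 1 states that departures from the protocol's analyses are set out in the SAP. None is recorded for physical examination.

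**SAP table shell.** Table 14.3.5 (Section 8, Mock Tables) lists Normal and Abnormal for each body system, with Abnormal split into clinically significant (CS) and not clinically significant (NCS). Its time points are given by "Programmer note: Visit x: Screening Visit, Visit 1, Visit 2, Visit 3, Visit 4 and Visit 5", and its denominator by "All Percentages rows are based on the total number of Safety Analysis Set". A row at each visit records whether the examination was performed. The shell has no shift or change rows.

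**ECG.** SAP 5.7 says "Descriptive summaries will be provided for the Electrocardiogram". The surviving footnote of Table 14.3.4 gives the visits: "Programmer Note: Visit x: Screening Visit, Visit 2 and Visit 5". The ECG is not named in the Protocol 9.4.2.1 sentence.

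**The concern.** The same patients are examined at up to six time points. In a single-arm safety study, the useful question about an examination is who was normal before dosing and abnormal afterwards. The protocol's change-from-baseline requirement addresses that question. A table of separate visit counts does not, because new abnormalities can be offset by resolutions and leave the totals unchanged.

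The denominator is a second, smaller problem in the same table. If counts at a late visit are divided by everyone ever dosed, a patient who has left is in the denominator but in neither result category. Percentages then drift down across visits even when nothing changes among the patients being examined. The SAP avoids this in Table 14.1.6, which bases percentages on N*, the patients at that visit. The fixed denominator in Table 14.3.5 is therefore a choice that can be changed.

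**Working it through.** **Inputs.** The footnote to SAP Table 14.1.1.1 gives 154 enrolled or screened, 10 screen failures, 124 completions, 20 discontinuations, 6 eligible patients not dosed, and 138 in the analysis set. SAP 3.4 defines the Safety set as those taking at least one dose.

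**1. Reproduce the SAP's count.**
- Eligible: 154 − 10 = 144, which equals 124 + 20.
- Dosed: 144 − 6 = 138, matching the SAP.
- Since 124 + 20 already accounts for all 144, the 6 undosed patients appear to be among the 20 discontinuations. That leaves 20 − 6 = 14 dosed patients who discontinued, and 14/138 = 10.1%.

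**2. Effect of the fixed denominator at Week 24.** Assume that all 124 completers and nobody else are examined. A rate p among those examined prints as p × 124/138 = 0.899p.

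| Rate among those examined | Printed over 138 | Shortfall (points) |
|---|---|---|
| 5% | 4.49% | 0.5 |
| 10% | 8.99% | 1.0 |
| 20% | 17.97% | 2.0 |
| 30% | 26.96% | 3.0 |

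The rates in the first column are illustrative; the documents give none. The Normal percentage shrinks by the same factor, so Normal plus Abnormal adds to about 89.9% instead of 100%.

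**3. What the visit counts can and cannot show.** Suppose that n patients are examined at both baseline and a later visit, with a abnormal at baseline and b abnormal later. The number newly abnormal lies between max(0, b − a) and min(b, n − a).
- n = 124, a = b = 12 (9.68% of 124): from 0 to min(12, 112) = 12 newly abnormal.
- n = 124, a = b = 37 (about 30%): from 0 to min(37, 87) = 37 newly abnormal.

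For these patients the later-visit line is the same wherever the truth lies in that range: 12/138 = 8.70% in the first case and 37/138 = 26.8% in the second.

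**4. Protocol and SAP side by side.**

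| Data | Protocol 9.4.2.1 asks for change | SAP plans change |
|---|---|---|
| Vital signs | Yes | Yes |
| Laboratory | Yes | Yes |
| Physical examination | Yes | No, and not declared |
| ECG | Not named | None named in 5.7; most of the Table 14.3.4 shell is not in the supplied text |

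**The case against.** **The protocol sentence cannot be applied literally.** It specifies means, SDs and percentiles, which have no meaning for a Normal/Abnormal rating, and the SAP supersedes the protocol where they differ. This is true, and it explains why the SAP authors turned to counts. It does not explain why change disappears altogether: a shift table is the categorical counterpart. Superseding the protocol also depends on the difference being described in the SAP, and it is not.

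**Clinically significant worsening is already captured.** This stands and limits the point. Protocol 8.1.1 and 8.1.2 cover aggravated as well as new findings, so a reader who inferred that important deterioration would go unreported would be wrong. What lacks a summary is mainly non-clinically-significant change and resolution, which appear only in Listing 16.3.6.

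**The denominator effect is visible and reversible.** This also stands. The row counting examinations performed lets a reader re-base the percentages. One might infer that the fixed denominator flatters safety by treating absent patients as normal. The shell does not do that, because both categories fall together.

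**No test is planned.** It is tempting to express the loss as statistical power. Protocol 9.1 and SAP 6.2 state that there is no hypothesis, and neither document plans a test on examination or ECG data. Power figures would compare tests that nobody intends to run.

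**Physical examination is not a listed endpoint.** Correct: it is not named among the primary or secondary endpoints. Protocol 9.4.2.1 nevertheless places this summary under the primary safety analysis.

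**Conclusion.** The point holds as a protocol-to-SAP mismatch for physical examination. The required change summary is missing, the omission is undeclared, and the planned table cannot identify newly abnormal patients. Its practical reach is mostly non-clinically-significant change and resolution.

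The denominator effect is modest: a relative reduction of about 10.1% at Week 24, or 1.0 point at a 10% rate and about 3 points at 30%. It rests on three assumptions: that only the 124 completers are examined at Week 24, that the 138 in the footnote are the Safety set, and that the abnormal rates are as illustrated.

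A reader might extend the criticism to ECG as a second departure from the protocol. The documents do not support that. Protocol 9.4.2.1 does not name ECG, and too little of the Table 14.3.4 shell is available to say what its columns contain. The fixed percentage denominator would in any case not affect means of ECG intervals, which use the observed readings.

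**What to change.** 1. **SAP 6.3.1 and Table 14.3.5.** For each body system, add a shift table from baseline to each post-baseline visit by Normal, Abnormal NCS and Abnormal CS. Restrict it to patients with both examinations, and report the number and percentage newly abnormal. Take baseline as the last examination before the first dose, in line with Protocol 9.4.1.
2. **Table 14.3.5.** Base the result percentages on patients examined at that visit, as Table 14.1.6 does with N*. Keep the row showing examinations performed.
3. **Optional, SAP 5.7 and Table 14.3.4.** If the full shell lacks it, add within-patient change from baseline in the ECG intervals at Visits 2 and 5, as a descriptive summary without a p-value.

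The data are already collected and listed (Listings 16.3.5 and 16.3.6). The cost is SAP wording, one revised table shell (two with the optional item), longer output, and a slightly smaller n in the paired summaries. No visit, measurement or patient is added.
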